5.5. Standardized questionnaires

Several standardized questionnaires will be administered to patients enrolled in the TONIC trial. Questionnaires will be administered at baseline (prior to randomization) and during follow-up at specified intervals (see Appendix 10.3 for the data collection schedule). The purpose of the questionnaires is to obtain important information regarding alcohol intake, nutrition, physical activity, health-related quality of life, and liver-related symptoms.

Alcohol questionnaires: Patients enrolled in the treatment protocol will complete the AUDIT questionnaire during screening. Patients will complete interim alcohol questionnaires (AUDIT-C) at follow-up visits (included in the Followup Medical History). The purpose of these questionnaires is to ascertain that there is no significant alcohol consumption at enrollment or during the study period and to evaluate the effect of alcohol consumption on the response to various interventions.

Nutrition Questionnaire: The Block Brief nutrition questionnaire will be administered to each patient during screening and after 48 and 96 weeks of treatment, and at the 120 week visit (24 weeks after withdrawal of study medication). This instrument is detailed and likely to take 30 minutes to complete. It estimates food frequency and quantity over the preceding 12-month period. The objectives of administering nutrition questionnaire are (a) to assess the baseline nutritional comparability among randomized patients and (b) to assess the possible effect of nutrient intake on the response to various treatments.

Measure of functional activity: The Modifiable Activity Questionnaire (MAQ) for Adolescents will be administered during screening and after 48 and 96 weeks of treatment, and at the 120 week visit (24 weeks after withdrawal of study medication).

Health-related quality of life: The Pediatric Quality of Life (PedsQL) questionnaire will be administered during screening and after 48, and 96 weeks of treatment, and at the 120 week visit (24 weeks after withdrawal of study medication).

Liver-related symptoms: A questionnaire on liver symptoms for children with NAFLD has been developed by the NASH CRN Measures and Assessments Committee and will be administered during screening and after 48 and 96 weeks of treatment, and at the 120 week visit (24 weeks after withdrawal of study medication).

The NASH CRN Steering Committee noted and acknowledged during the questionnaire selection process that some questionnaires were not validated for all eligible participants in TONIC trial.

5.6. Specimen repository

Specimens will be collected and stored in a central repository for use as approved by the Steering Committee of the NASH CRN (see Appendix 10.4 for whole blood draw schedule). Specimens include serum, plasma, and DNA. The blood collected into a serum separation tube at screening visit 2, and at 24, 48, 72, and 96 week visits will be divided into 0.5 mL aliquots. Aliquots will be kept in a storage facility at -70°C . Blood will be collected at the screening visit 2 for extraction of DNA which will be stored at -20°C .

5.7. Overview of scoring of liver biopsies

Liver biopsies will be obtained from each patient in the 6 months prior to randomization and after 96 weeks of treatment. Standard of care baseline liver biopsies will be reviewed and scored by the local NASH CRN pathologist to determine eligibility. Standard of care slides accessed with patient's permission and shipped to the Histology Review Center will be scored by central review of the slides by the Pathology Committee. TONIC trial follow-up liver biopsy slides will be reviewed and scored by the local NASH CRN pathologist first for patient care (data not collected) and then shipped to the Histology Review Center for scoring by central review of the slides by the Pathology Committee.

The tissue will be examined by light microscopy and scored based upon the NASH CRN NAFLD/NASH scoring system. The scoring system is detailed in the Liver Biopsy Procedure and NAFLD/NASH Histologic Scoring System Manual prepared by the NASH CRN Pathology Committee and approved by the NASH CRN Steering Committee. Pediatric and adult biopsies will be scored according to the same criteria. However, since change in histology is not the primary outcome for TONIC trial and since children may show a different pattern of progression than adults, criteria for improved histology in children will not be specified at this time. Briefly, biopsies will be assessed for the following:

- (1) Adequacy of the biopsy sample for reading;
- (2) Steatosis (including grade of 0-3, location, and whether microvesicular);

- (3) Fibrosis based upon Masson's trichrome stain as 0-4 with:
 0 = none
 1a = mild zone 3 perisinusoidal
 1b = moderate zone 3 perisinusoidal
 1c = portal/periportal only
 2 = zone 3 and periportal
 3 = bridging
 4 = cirrhosis
- (4) Lobular inflammation as 0, 1 (<2 areas seen), 2 (2-4 areas seen), or 3 (>4 areas seen under 20-fold magnification) and as presence or absence of microgranulomas and lipogranulomas
- (5) Portal inflammation as 0 (none), 1 (mild), or 2 (greater than mild)
- (6) Liver cell injury: Ballooning as 0 (none), 1 (few) and 2 (many), with notation of presence or absence of acidophilic bodies (0 = rare or 1 = many), pigmented macrophages (0 = rare/absent, 1 = many), and megamitochondria (0 = rare/absent, 1 = many)
- (7) Mallory bodies as 0 (rare/absent) or 1 (many)
- (8) Glycogen nuclei as 0 (rare/absent) or 1 (many)
- (9) Hepatocellular iron grade based on iron stain as 0 (absent or barely discernible, 40x), 1 (barely discernable granules, 20x), 2 (discrete granules resolved, 10x), 3 (discrete granules resolves, 4x), and 4 (masses visible by naked eye)
- (10) Steatohepatitis as 0 (no), 1a (suspicious/borderline/indeterminate; Zone 3 pattern), 1b (suspicious/borderline/indeterminate; Zone 1, periportal pattern), and 2 (yes, definite)

The steatosis grade 1 or greater will be used to determine eligibility and all component scores will constitute secondary histologic outcome measures defined elsewhere in this protocol. Baseline liver biopsies will be scored by the local NASH CRN pathologist for eligibility. Baseline and follow-up liver biopsies will be scored by central review of the slides by the Pathology Committee. The scores obtained centrally will be used for data analysis.

5.8. Adherence and retention

Two important goals of this protocol are to optimize adherence to the pharmacological regimen and to maximize the retention of participants in the study. Assessment of adherence to the assigned study drug will provide clinic staff a means to identify participants having problems with adherence. Adherence will be assessed by:

- Counts of pills in the patient's returned pill containers
- Conducting a brief, structured interview, the study coordinator will assist the patients to identify problems in taking the study drug and to estimate adherence to the assigned study drug since their previous visit.

TONIC Trial Protocol

These assessments will guide the consideration of strategies to improve adherence. Resources will be provided to remove barriers to participation such as child or elder care, transportation, and parking expenses. These resources can be provided as cash, transportation vouchers, or parking passes.

Certificates of appreciation may be given at enrollment and at conclusion as an incentive.

5.9. Management of concomitant conditions

Hypertension and hyperlipidemia will be managed in conjunction with the patient's primary care physician according to the protocols described in the Standards of Care document prepared by the Standards of Care Committee of NASH CRN.

General anesthesia during major surgical procedures may pose a risk of metabolic acidosis. Study drug will be suspended prior to such anticipated surgical procedures, with the last dose administered on the day prior to surgery. Serum creatinine should be less than 1.5 mg/dL for males and less than 1.4 mg/dL for females to restart the study drug after the surgical procedure.

In the event of major dermatological reactions such as generalized urticaria, bullous rashes, exfoliative dermatitis, or Stevens-Johnson Syndrome, study drug will be discontinued immediately and not restarted. For local skin reactions, study drug may be discontinued if the skin reactions are potentially drug related. If the rashes clear, the study drug may be restarted at once daily dosage and then progressing to twice daily dosage after another two weeks. If local skin reactions recur with restarting the study drug, study drug should be discontinued. In cases where the study drug has been discontinued, the study drug will be unmasked and the patient, investigator, and primary care provider will be notified in order to prevent future exposures.

TONIC Trial Protocol

6. Safety monitoring

Safety issues can be divided into adverse effects relating to the therapeutic interventions, safety issues related to liver biopsy, concerns related to patient privacy, and issues related to the central specimen repository.

6.1. Safety issues related to metformin

The following paragraphs discuss the important potential adverse effects of metformin and the proposed safeguards to minimize the risks involved.

- **Gastrointestinal side effects:** As many as 30% of patients receiving metformin report diarrhea, nausea, metallic taste, abdominal bloating, flatulence, or anorexia. We intend to minimize these side effects by recommending that metformin be taken with food and by gradually titrating the dose over two weeks.
- **Anemia:** About 6-9% of patients receiving metformin may develop reduced vitamin B12 levels. However, megaloblastic anemia is rare and metformin use has not been reported to cause peripheral neuropathy. Vitamin B12 levels will be measured at baseline and every 24 weeks until the end of TONIC trial. Patients with low B12 levels at baseline or those with diminishing B12 levels while on the protocol will be treated according to standard clinical practice.
- **Lactic acidosis** is a rare, but serious, metabolic complication that can occur due to metformin accumulation during treatment with metformin. The reported incidence of lactic acidosis in patients receiving metformin is very low (approximately 0.03 cases/1,000 patient years). However, when it occurs, the case fatality rate is 50%. We intend to minimize the lactic acidosis risk (a) by not enrolling patients with renal dysfunction in TONIC trial, (b) by not including patients with cirrhosis of the liver, and (c) by thoroughly educating the patients and investigators about avoiding intravenous contrast during the study period. If intravenous contrast is required either electively or emergently, patients will discontinue study drug on the day of dye administration for 3 days. The study drug will be restarted if the serum creatinine measured 48 hours after the contrast administration is less than 1.5 mg/dL for males and less than 1.4 mg/dL for females.

Patients in whom the study drug has been discontinued due to significant adverse effects will be followed according to the protocol and will be offered a liver biopsy at the conclusion of the study.

6.2. Safety issues related to vitamin E

From numerous publications on the “prophylactic” and “therapeutic” use of vitamin E, it may be concluded that the toxicity of vitamin E is very low. It has been demonstrated in animal experiments that vitamin E has neither mutagenic, teratogenic nor carcinogenic properties. Based on studies in humans, a daily dosage of 100-300 mg vitamin E can be considered harmless from a toxicological point of view. Using double-blind studies involving a large number of subjects, it has been demonstrated that oral doses up to 3,200 units/day led to no consistent adverse effects^{37,38,39}. From a large body of published data, dosage ranges have been deduced which can be characterized as safe for human subjects even where their use extends over a long period of time. Oral intake of high levels of vitamin E can exacerbate the blood coagulation defect of vitamin K deficiency caused by malabsorption or anticoagulant therapy. High levels of vitamin E intake in these subjects are therefore contraindicated.

In the Diabetes Prevention Program (DPP), the incidence of diabetes in the adult aged placebo group was 11.0 cases per 100 person years⁴². Based on this, it is anticipated that approximately 13 subjects in the placebo group will develop new-onset diabetes mellitus during their participation in the TONIC trial. Although use of antioxidants may improve insulin resistance and thereby may reduce the incidence of new-onset diabetes, it is safe to assume that the magnitude of risk of new-onset diabetes mellitus in patients randomized to vitamin E is same as placebo (ie, 13 subjects during the 24 months treatment). Measures to identify patients who have developed new-onset diabetes mellitus and their management strategy are described in section 6.3.

6.3. Safety issues related to placebo

As presented in the section above, it is anticipated that about 13 subjects in the placebo group will develop new-onset diabetes mellitus during their participation in the TONIC trial. Participants will be seen frequently during the study period for assessment of symptoms consistent with uncontrolled hyperglycemia and will have fasting glucose levels measured at 24, 48, 72, 96, and 120 weeks after randomization (at 48, 96, and 120 weeks this measurement is part of OGTT). Patients with fasting glucose ≥ 126 mg/dL will have the same test repeated within 6 weeks to confirm the diagnosis of new-onset diabetes. Patients with a diagnosis of new onset diabetes will be managed according to the following stepped care approach and the primary care physician will be notified.

- (a) Lifestyle counseling to reduce excess body weight and increase exercise
- (b) Education on diabetic diet
- (c) If fasting glucose remains greater than 140 mg/dL after three months or if patient develops symptomatic diabetes, treatment with sulfonylurea will be initiated.
- (d) If patient still is unable to maintain glycemic control, primary care physician may request unmasking of the study medication and should institute necessary measures for diabetes management. Study medication will not be unmasked to the investigator. These patients will be followed at scheduled intervals to collect other outcome data; however, they will

not have the OGTT scheduled for the visits at 48, 96, and 120 weeks but will have only fasting glucose levels measured.

During the trial, if a participant develops side effects thought to be due to the study drug and requires cessation of study drug, the medication will be stopped for 4 weeks. If the side effects disappear, an attempt will be made to reintroduce the study medication after 4 weeks. If the symptoms reappear, study medication will be once again stopped and the patient will no longer receive the study medication, but will be followed in the study according to the protocol, in keeping with the “intention-to-treat” paradigm.

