- Females of childbearing potential: breast feeding
- Any other condition, which in the opinion of the investigator would impede compliance or hinder completion of study

Outcome measures

- Primary: Sustained reduction in ALT to either 50% of baseline value or ≤ 40 U/L
- Secondary:
 - Sustained reduction in serum AST
 - Sustained reduction in serum GGT

TONIC Trial Protocol

Design synopsis

- Change in histologic feature scores determined by standardized scoring of liver biopsies at baseline and after 96 weeks of treatment
- Change in liver fibrosis, inflammation, or steatosis
- Change in body mass index
- Change in insulin resistance indices
- Change in serum vitamin E levels
- Change in serum cytokine and fibrosis marker levels
- Change in serum lipid profile
- Change in QOL scores

Randomization

- Centrally administered randomization stratified by clinical center and blocked by calendar time

Visit schedule

- Baseline/screening: at least 1 visit separated by at least 1 calendar day from randomization; screening period can last no more than 16 weeks (112 days)
- Randomization (final pre-treatment interview, dispensing of study drugs)
- Follow-up visits
 - 4 weeks after randomization
 - 12 weeks after randomization and every 12 weeks thereafter up to 96 weeks
 - 120 weeks after randomization (24 weeks after treatment ends)
- Liver biopsy at 96 week visit

Statistical analysis

- All analyses will be on an “intention-to-treat” basis

Safety monitoring

- NIDDK appointed Data and Safety Monitoring Board will monitor the data for safety and efficacy for outcomes such as metabolic acidosis, hepatotoxicity, hypoglycemia, pregnancy, new onset diabetes, and any other outcomes or events identified as safety-related
-

TONIC Trial Protocol

1. Objectives

Insulin resistance and oxidative stress (resulting in lipid peroxidation) are considered to be the two most important mechanisms in the pathogenesis of NAFLD. We hypothesize that metformin and vitamin E will lead to sustained reduction in serum ALT with biopsy proven NAFLD through changes in insulin resistance or oxidative stress.

The principal objective of this randomized, multicenter, double-masked, placebo-controlled trial is to evaluate whether 96 weeks of treatment with either metformin or vitamin E leads to sustained reduction in serum ALT in nondiabetic children with NAFLD compared to treatment with placebo.

Other objectives include:

- To evaluate changes in serum AST and GGT

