4.3. Exclusion criteria

Patients who satisfy any of the following exclusion criteria will be ineligible for enrollment in the trial:

- History of significant alcohol intake (AUDIT questionnaire) or inability to quantify alcohol consumption
- Diabetes mellitus
 - Fasting serum glucose of 126 mg/dL or greater
 - OR
 - 2-hour serum glucose of 200 mg/dL or greater from oral glucose tolerance test (OGTT) with 2 g/kg (maximum 75 g) glucose load
 - OR
 - History of diabetes mellitus
- ALT > 400 U/L on measurement closest in time to randomization
- Clinical or histologic evidence of cirrhosis
- Evidence of other chronic liver disease
 - Alpha-1 antitrypsin deficiency
 - Bile duct anomalies
 - Hemochromatosis
 - Hepatitis - autoimmune or viral
 - Wilson disease
- Serum creatinine of 1.5 mg/dL or greater for males and 1.4 mg/dL or greater for females
- Use of drugs historically associated with NAFLD (systemic glucocorticoids, tetracyclines, anabolic steroids, valproic acid, salicylates, tamoxifen, other known hepatotoxins) for more than 2 weeks in the 2 years prior to randomization
- Use of antidiabetic drugs (insulin, biguanides, sulfonylureas, metformin, thiazolidinediones) in the 3 months prior to randomization

- Use of antiNAFLD drugs (metformin, vitamin E, thiazolidinediones, UDCA, SAM-e, betaine, milk thistle, probiotics) in the 3 months prior to randomization
- Use of any over-the-counter or herbal remedy for hyperlipidemia in the 3 months prior to randomization
- History of metabolic acidosis
- History of renal dysfunction
- History of coagulopathy
- History of bariatric or hepatobiliary surgery
- History of total parenteral nutrition during the past 3 years prior to screening
- Inability to swallow study medication
- Vitamin E supplementation of greater than 100 I/U per day
- Disease considered by study physician to be significant
- Females of childbearing potential: positive pregnancy test during screening or at randomization or unwillingness to use an effective form of birth control during the trial
- Females of childbearing potential: breast feeding
- Any other condition, which in the opinion of the investigator would impede compliance or hinder completion of study

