- **Week 36 visit:** Interim history including review of medications and adverse effects; height, weight, waist and hip measurements, vital signs (temperature, heart rate, blood pressure), focused physical examination; blood draw for metabolic panel (sodium, potassium, chloride, bicarbonate, calcium, phosphate, BUN, creatinine, uric acid, albumin, total protein) and hepatic panel (total and direct bilirubin, AST, ALT, alkaline phosphatase); urine pregnancy test (for patients of childbearing potential).
- **Week 48 visit:** Blood sample for fasting serum glucose, insulin, and C-peptide will be obtained after an overnight fast. After administration of glucose solution in a dose of 2 g per kilogram of body weight (up to a maximum of 75 g), blood sample for 2-hour serum glucose and insulin will be obtained for the OGTT. Interim history including review of medications and adverse effects; height, weight, waist and hip measurement, triceps skin fold thickness, mid-upper arm circumference; vital signs (temperature, heart rate, blood pressure), detailed physical examination including Tanner staging and acanthosis nigricans staging; blood draw for CBC, metabolic panel (sodium, potassium, chloride, bicarbonate, calcium, phosphate, BUN, creatinine, uric acid, albumin, total protein), hepatic panel (total and direct bilirubin, AST, ALT, alkaline phosphatase), GGT, prothrombin time, fasting lipid profile (total cholesterol, triglyceride, LDL, HDL), HbA1c, vitamin B12, free fatty acid, leptin, C-reactive protein; urine pregnancy test (for patients of childbearing potential); alcohol, nutritional, physical activity, HR-QOL and liver symptom questionnaires; blood draw for banking at central repository.

- **Week 60 visit:** Interim history including review of medications and adverse effects; height, weight, waist and hip measurements, vital signs (temperature, heart rate, blood pressure), focused physical examination; blood draw for metabolic panel (sodium, potassium, chloride, bicarbonate, calcium, phosphate, BUN, creatinine, uric acid, albumin, total protein) and hepatic panel (total and direct bilirubin, AST, ALT, alkaline phosphatase); urine pregnancy test (for patients of childbearing potential).

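### New-onset diabetes on study has only a fasting-glucose rule, while entry also uses 2-hour glucose, so capture of children positive only on the scheduled OGTT is not ensured in a DSMB-monitored outcome

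*Supplement*

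**What the plan says.** **At entry.** Section 4.3 (and the Design synopsis) excludes a child as diabetic on any one of three grounds. Two are a known history of the disease and a fasting value at or above 126 mg/dL. The third is a post-load criterion, worded as "2-hour serum glucose of 200 mg/dL or greater from oral glucose tolerance test (OGTT) with 2 g/kg (maximum 75 g) glucose load".

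**On study.** Section 6.2 sends the reader to 6.3 for case finding: "Measures to identify patients who have developed new-onset diabetes mellitus and their management strategy are described in section 6.3". Section 6.3 schedules fasting glucose at weeks 24, 48, 72, 96 and 120 and notes that "at 48, 96, and 120 weeks this measurement is part of OGTT". Its diagnostic sentence is: "Patients with fasting glucose ≥ 126 mg/dL will have the same test repeated within 6 weeks to confirm the diagnosis of new-onset diabetes". Stepped care follows. The later 140 mg/dL thresholds, in step (c) of 6.3 and in the unmasking rule of 6.9, are also fasting values.

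**The 2-hour value.** Section 5.4 collects it at weeks 48, 96 and 120: "blood sample for 2-hour serum glucose and insulin will be obtained for the OGTT". Appendix 10.3 agrees. Section 6.3(d) drops the OGTT for children with new-onset diabetes whose glycemic control still fails.

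**Monitoring.** The Design synopsis has the DSMB monitor outcomes such as "metabolic acidosis, hepatotoxicity, hypoglycemia, pregnancy, new onset diabetes". Sections 6.2 and 6.3 forecast about 13 new cases in the placebo group, and 6.2 assumes the same number on vitamin E.

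**The concern.** The protocol uses two sets of glucose criteria for one condition, and the on-study set omits a measurement that the trial takes at three follow-up visits. A child can hold values that would have barred entry as diabetic and yet trigger no repeat test and meet no stated case rule.

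New-onset diabetes is a named safety outcome, to be compared across arms that include an insulin-sensitizing drug. If a study drug shifts fasting and post-load glucose differently, a count based on fasting glucose alone may not be neutral between arms. The documents do not show that it would be biased. Without both counts, nobody can tell. The trial also describes its population as nondiabetic, and that word would mean one thing at screening and another afterwards.

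**Working it through.** **Step 1. Compare the criteria.**

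| | Entry (4.3) | On study (6.3) |
|---|---|---|
| Fasting glucose | at least 126 mg/dL | at least 126 mg/dL, same test repeated within 6 weeks |
| 2-hour OGTT glucose | at least 200 mg/dL | no rule |
| Relation | either is enough | fasting only |
| Repeat test in the criterion | none stated | required |

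There are two differences: the missing 2-hour criterion and the added repeat test.

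**Step 2. Follow one illustrative child.** Take fasting 110 and 2-hour 215 mg/dL. At screening, 215 is at least 200, so the child is excluded. At week 48, 110 is below 126, so 6.3 asks for no repeat test. The fasting value is also below 140, so neither step (c) of 6.3 nor the unmasking rule in 6.9 is reached on glucose. No section says what follows from the 215.

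**Step 3. Look for another use of the 2-hour glucose.** Section 7.2 assesses insulin resistance by HOMA, which the glossary computes from fasting insulin and fasting glucose. Section 7.6 gives the DSMB no diabetes case definition. No diabetes rule uses the 2-hour glucose, and neither does HOMA.

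**Step 4. Reproduce the planning figure.** Inputs: 60 children per group (7.5), 11.0 cases per 100 person-years (6.2), 24 months of treatment (6.2).

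60 × 0.11 × 2 = 13.2, against a stated 13. It reproduces. With an exponential risk, 60 × (1 − exp(−0.22)) = 11.8, which is close.

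**Step 5. Size, by assumption only.** The documents do not give the share *s* of cases that show only on the 2-hour value. If 13.2 covers both criteria, the number outside the fasting rule is 13.2 × *s*:

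| *s* | Outside the rule, per group | Meeting the rule, per group |
|---|---|---|
| 10% | 1.3 | 11.9 |
| 20% | 2.6 | 10.6 |
| 30% | 4.0 | 9.2 |
| 50% | 6.6 | 6.6 |

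That is about 1 to 7 children in a group of 60. Three limits apply.

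- The rate comes from an adult trial whose case definition is not shown. If 13.2 were instead a fasting-only figure, the total would be 13.2 / (1 − *s*), or 14.7 at 10% and 26.4 at 50%. The additional cases would then be 1.5 to 13.2.
- Some of these children could meet the fasting rule at a later visit. They would be late, not lost.
- The forecast covers the 24-month treatment period, which contains the week 48 and week 96 OGTTs. The week 120 OGTT falls 24 weeks after treatment ends.

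**The case against.** A reader might infer that OGTT-only cases are excluded from the DSMB outcome and that fasting glucose is the only route to a diagnosis. The documents do not support either reading.

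- No section says that the DSMB or final tables count diabetes by the 6.3 rule. That sentence says when to repeat a test and leads into stepped care.
- Section 6.8 defines adverse events broadly and requires them to be recorded whether or not they are thought drug-related. Section 7.6 lets the DSMB request safety measures. A 2-hour value of 215 could reach the board.
- Section 6.3 adds a clinical route: "Participants will be seen frequently during the study period for assessment of symptoms consistent with uncontrolled hyperglycemia". Step (c) acts on symptomatic diabetes, and HbA1c is measured at weeks 48, 96 and 120.

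These points stand, and they limit the claim to capture that is not ensured. They do not remove it. No diagnostic threshold is attached to symptoms or HbA1c, and no 2-hour result is made reportable. Whether such a child is reported would rest on judgment at eight centers.

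It would also be too strong to say that every child has a 2-hour value at all three visits, given the waiver in 6.3(d), or that incidence is shown to be understated in every arm.

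A stricter on-study rule may be deliberate. A confirmatory repeat is easy to understand. It does not explain the silence on a result that the trial itself treats as diabetes at entry, and no reason is given.

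**Conclusion.** The mismatch between 4.3 and 6.3 is in the text and needs no assumption. The only on-study diagnostic threshold stated is a repeated fasting glucose of at least 126 mg/dL. A child who meets only the 2-hour criterion meets no stated case rule, so inclusion in a named safety outcome is neither ensured nor uniform across centers.

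The size cannot be derived from the documents. The range of about 1 to 7 children per group rests on an assumed share of 10% to 50% and on reading the 13 as covering both criteria, and it includes children who would only be identified later. Any distortion between arms is conditional and unquantified.

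The scope is safety reporting. The primary ALT comparison, its error rate and its sample size are not affected. The point is worth correcting because the data are already scheduled for collection.

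**What to change.** In the DSMB reports and final safety tables, show two counts of new-onset diabetes by arm, side by side:

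1. children who meet the 6.3 rule, that is, a confirmed fasting value;
2. children who meet either entry glucose criterion of 4.3 at any scheduled on-study measurement.

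In the second count, flag confirmed against unconfirmed results, because the entry criteria state no repeat test and this count relaxes confirmation for fasting values as well as admitting single 2-hour values. Also flag children whose OGTT was waived under 6.3(d), for whom the 2-hour criterion cannot be applied at later visits.

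Separately, the sponsor must reconcile 4.3, 6.3 and 6.9 on how on-study 2-hour results are handled. Which findings should prompt clinical action is for the sponsor to settle, and no clinical rule is proposed here.

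**Cost:** a wording change and one more table row with flags. No new tests are needed. The downside is a higher reported count that includes unconfirmed single values, which is why the two counts should stay separate.
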